9. STATISTICAL CONSIDERATIONS

9.1 General Considerations

The statistical analysis plan (SAP) will be finalized and submitted to the appropriate health authorities before any interim analysis or unblinding occurs. The primary unblinded statistical analyses will be conducted by the sponsor or authorized representative after all enrolled study subjects who remain active in the trial at the time of their 24 month study visit have completed this milestone event.

Interim analyses may be performed during the course of the trial. These will be conducted by external independent statistician(s) who will be unblinded to study data. All blinded personnel and subjects will remain blinded to the results of the analyses. The integrity of the study database will be maintained as well, and no bias will be introduced to the evaluations in the study due to the conduct of these interim analyses.

The details of interim analyses are outlined in the Statistical Analysis Plan (SAP). All subjects, independent reviewers and blinded personnel interacting with subjects will remain blinded through the completion of the study.

[figure not shown]
The primary efficacy objective of the study is to demonstrate that either rexlemestrocel-L alone or rexlemestrocel-L + HA has a higher rate of treatment success—defined as 50% reduction in low back pain VAS score, 15 point decrease in ODI score, and no interventions at the treated disc—compared to the saline control arm at 12 *AND* 24 months post-treatment. The significance level for the Primary Efficacy Endpoint is adjusted for multiple comparisons of each active

treatment arm to the control group. The family-wise type I error rate will be controlled below one-sided 0.025. Additional details, including the adjusted threshold for primary analysis success, will be finalized in the SAP.

For secondary endpoints, a gatekeeping strategy will be used to maintain the overall type 1 error at overall one-sided 0.025. For all other exploratory efficacy endpoints, the significance level of two-sided 0.05 will be used for comparison between each active arm and the control group.

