9.6.2 Primary Efficacy Analysis

The Primary Efficacy Endpoint for overall treatment success (responder vs non-responder) at 12 *AND* 24 months will be summarized for each treatment by numbers and percentages. Each active treatment arm will be compared to the saline control group using a Bayesian test of superiority using non-informative Beta (0.5, 0.5) priors for each arm. An arm will be considered superior to the saline arm if there is sufficiently high posterior probability that the response rate of that arm is higher than the saline control arm. The posterior probability threshold is Bonferonni-adjusted to account for multiple comparisons. The value of the posterior probability threshold for success will be discussed in the study statistical analysis plan (SAP).

The rationale for using a Bayesian approach for the primary analysis is that we are already using Bayesian methodology for multiple imputation of missing data (see Section 9.9). Keeping the Bayesian methodology for the primary analysis ensures a consistent framework that naturally synthesizes the multiply imputed outcomes into the posterior distribution. In this way, the uncertainty due to missing data is naturally incorporated into the inference, without the cumbersome necessity of combining p-values as in a frequentist framework. The methods for handling missing data are discussed in Section 9.9.

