9.6.3 Secondary and Other Efficacy Analyses

The same Bayesian methodology used for the primary analysis will also be used for the secondary endpoints. The Bonferroni-adjusted posterior probability threshold of 0.9875 will apply to any subsequent secondary analyses performed.

As part of the gatekeeper strategy, the evaluation will be carried out in a hierarchical fashion following the order given below. Specifically, if the primary endpoint objective is met, the secondary outcomes will be evaluated hierarchically within each arm using the posterior probability threshold of 0.9875 for each comparison, sequentially. Once a key secondary endpoint is not met at this threshold within an arm, all subsequent comparisons in that arm will be considered exploratory.

- Pain Responder at both 12 AND 24 months: Measured as subjects meeting at least a 50% decrease from baseline in low back pain VAS score (average pain over 24 hours) at both Study Visit 6 (12 months post-treatment) and Study Visit 8 (24 months posttreatment) with no adjudicated post-treatment intervention through Study Visit 8.
- Functional Responder at both 12 AND 24 months: Measured as subjects meeting at least a 15-point decrease from baseline in ODI at both Study Visit 6 (12 months posttreatment) and Study Visit 8 (24 months post-treatment) with no adjudicated posttreatment intervention through Study Visit 8.
- 3. Treatment Success at 24 months: Measured as subjects meeting each of the following criteria at Study Visit 8 (24 months post-treatment):
 - a. at least a 50% reduction from baseline in low back pain VAS score (average pain over 24 hours); AND
 - b. at least a 15 point decrease from baseline ODI score; AND
 - c. no interventions at the treated level
- 4. Minimal Pain Responder at 24 Months: Measured as subjects meeting low back pain VAS score (average pain over 24 hours) of 20mm or less at Study Visit 8 (24 months post-treatment) with no adjudicated post-treatment intervention through Study Visit 8.
- 5. Minimal Disability Responder at 24 Months: Measured as subjects having an ODI score of 20% or less at Study Visit 8 (24 months post-treatment) with no adjudicated post-treatment intervention through Study Visit 8.
- 6. Time to first intervention over 24 months: Measured as time to first post-treatment intervention at the treated level through 24 months post-treatment.

CONFIDENTIAL

Mesoblast

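### Once one active arm has met its primary and all six secondaries, half of the one-sided 0.025 goes unused, because no readable text passes that arm's 0.0125 to the other arm

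*Combined protocol and SAP*

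**What the plan says.** Section 9.1 sets the error target for the primary: "The family-wise type I error rate will be controlled below one-sided 0.025". For the secondaries it adds: "For secondary endpoints, a gatekeeping strategy will be used to maintain the overall type 1 error at overall one-sided 0.025". The primary objective in the same section is "to demonstrate that either rexlemestrocel-L alone or rexlemestrocel-L + HA has a higher rate of treatment success" than saline, so a win in one arm is enough.

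Section 9.6.2 says of the primary test: "The posterior probability threshold is Bonferonni-adjusted to account for multiple comparisons". It leaves the numerical value to the SAP, whose text is not in the document available here.

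Section 9.6.3, repeated in the Statistical Analysis part of the synopsis, is explicit for the secondaries: "The Bonferroni-adjusted posterior probability threshold of 0.9875 will apply to any subsequent secondary analyses performed". Six endpoints follow in fixed order, and "the secondary outcomes will be evaluated hierarchically within each arm using the posterior probability threshold of 0.9875 for each comparison, sequentially". The stopping rule is local to the arm: "Once a key secondary endpoint is not met at this threshold within an arm, all subsequent comparisons in that arm will be considered exploratory". The first five endpoints are responder rates. The sixth, time to first intervention, is compared by a log-rank test stratified by site.

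No readable section says what happens to an arm's share of the error rate when that arm has met everything in its sequence.

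**The concern.** In a fixed sequence run at 0.0125, the level is carried from each endpoint met to the next. After the seventh test (the primary plus six secondaries) there is nothing left to carry it to. A Bonferroni-based graphical procedure would then add it to the other arm's level. As readable, the plan lets it lapse, so the second arm stays at 0.9875 even when only that arm can still produce a false claim and 0.025 is allowed.

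At stake are the second arm's primary and secondary claims. Section 1.6.2 gives the rexlemestrocel-L alone arm a purpose of its own (whether HA adds anything, and whether the cells alone give benefit), so the second claim is of real interest.

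**Working it through.** **1. The plan's figure.** 1 − 0.025/2 = 0.9875, and 0.0125 + 0.0125 = 0.025. The stated threshold reproduces exactly as an equal split over two comparisons with saline. For the primary, 0.9875 is inferred from the Bonferroni wording.

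**2. Why transfer is allowed.** Call the arms A and B, with an end-of-chain transfer from A to B.
- If any null hypothesis in A's chain is true, the transfer happens only after A has wrongly rejected it. An error has then already been counted, and the transfer adds no new error event.
- If all of A's nulls are false, only B can err. Its first true null is tested at 0.025 at most.
- If both arms have true nulls, the bound is 0.0125 + 0.0125 = 0.025.

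Every claim made under the present rule is still made, because no test becomes stricter.

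**3. Error rates.** Two seven-step chains were simulated 1,000,000 times with normal statistics. The between-arm correlation was 0.5 (shared control, 1:1:1), and within-arm correlations of 0, 0.5 and 0.8 were assumed. The gate was per arm.

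| True state | As written | With transfer |
|---|---|---|
| All nulls true | 0.023 | 0.023 |
| A fully effective, B null throughout | 0.0124 | 0.0246 |
| A fully effective, B effective on the primary only | 0.0124–0.0125 | 0.0249 |

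The largest value with transfer over the six configurations tried was 0.0249.

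**4. Power gain, first model.** Assumptions: 120 per arm (section 3.1), primary success 21–24% on saline and 37–44% on active, interventions in 12–20% against 7–12%, the primary also at 0.9875, and 0.977 after transfer. Endpoint 6 was approximated by the proportion free of intervention. There were 48,000 trials per scenario.

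| Second arm's primary | Gain (points) | Both arms succeed | Gain (points) |
|---|---|---|---|
| 0.878 → 0.893 | 1.5 | 0.798 → 0.827 | 2.9 |
| 0.881 → 0.887 | 0.6 | 0.802 → 0.814 | 1.2 |
| 0.862 → 0.865 | 0.3 | 0.771 → 0.777 | 0.6 |
| 0.655 → 0.669 | 1.4 | 0.501 → 0.529 | 2.8 |
| 0.711 → 0.759 | 4.8 | 0.693 → 0.742 | 4.9 |

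**5. Power gain, second model.** This is the normal model of step 3 with equal standardised effects of 2.24 to 3.6 on all endpoints and a nominal 0.975 after transfer. The second arm's primary power rises by 1 to 3 points overall, for example 0.841 to 0.862–0.868 at an effect of 3.24. Given that the first arm passed all seven tests, it rises by 3 to 9 points (0.945 to 0.971 at 3.6; 0.730 to 0.819 at 2.24). The chance that at least one arm meets its primary is identical with and without transfer (0.9375 at 3.24).

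**6. What limits the trigger.** Exact power at 0.9875 with 120 per arm, for the proportion free of intervention as a stand-in for endpoint 6, is 0.79 for intervention rates of 20% against 7%, 0.30 for 20% against 12%, and 0.19 for 12% against 7%. When these rates differ little, few chains complete and little is passed on.

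**7. An illustration.** Take assumed counts of 26/120 on saline and 40/120 or 41/120 on the second arm. The posterior probability of superiority under Beta(0.5, 0.5) priors is 0.979 or 0.985. Both miss 0.9875, and both pass 0.977.

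**8. Why the post-transfer threshold is not simply 0.975.** Exact size by binomial enumeration, true rates 0.10 to 0.70:
- 120 per arm: 0.0227–0.0269 at 0.975; 0.0220–0.0239 at 0.977.
- At 0.977, the maximum is 0.0252 with 110 per arm and 0.0258 with 100 per arm.

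The existing 0.9875 is also only nominal. Its exact size at 120 per arm is 0.0125–0.0135 for control rates of 10–40%.

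**The case against.** The strongest reply is that this is a preference. Bonferroni between arms with a fixed sequence within each is standard, simple and valid, and it keeps each arm's claims independent of the other's results. The objective needs only one arm to succeed, and transfer does not alter that probability. Four of the five scenarios in step 4 gain 1.5 points or less on the second arm's primary, and all inputs other than the arm size are assumed: the readable text gives no saline rate, intervention rate or design power, only 44.4% on 6 million cells in the earlier study (section 1.6.3). The SAP may set another primary threshold, an interim adjustment or a transfer rule of its own.

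Most of this stands as a limit on size. It does not remove the point, since the alternative makes every claim the present rule makes, and sometimes more, within the same 0.025. Independence of the two arms' claims is a real property that would be given up.

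Two stronger readings are tempting. A reader might infer that the trial loses power for its stated objective; step 5 shows that it does not. A reader might also infer that error control fails. With a per-arm gate it does not. The gate wording is loose, though: section 9.6.3 opens the secondaries when the primary objective is met, and that objective is satisfied by one arm. If one arm's win opened both arms' secondaries, simulated family-wise error would reach 0.030–0.037 in some configurations. The within-arm testing language points to the per-arm reading, so the documents do not establish a breach, but the gate should be settled before any transfer is added.

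**Conclusion.** The point holds as a modest efficiency gain, not as a fault in validity. With a per-arm gate, the plan controls error at a nominal 0.025 but uses only about 0.0125 of it once one arm has met all seven endpoints. Under the assumed effects, passing the level on is worth roughly 0.3 to 5 points for the second arm's primary and for the chance that both arms succeed. The gain is least when intervention rates differ little, and nothing is gained for the chance that at least one arm wins.

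This rests on assumed response rates, intervention rates and endpoint correlations, on a primary threshold of 0.9875 that is inferred, and on the SAP containing no transfer rule.

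**What to change.** Amend section 9.6.3 and the SAP before any interim analysis or unblinding:

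1. State that an arm's secondaries are tested only if that same arm meets its primary.
2. When one active arm has met its primary and all six secondaries, pass its level to the other arm, which is then tested at one-sided 0.025 from its first endpoint not yet met.
3. For the log-rank endpoint, give one-sided p-value cut-offs: 0.0125, and 0.025 after transfer.
4. For the Beta(0.5, 0.5) endpoints, set the post-transfer posterior threshold by exact calculation at the actual arm sizes so that size does not exceed 0.025. It is about 0.977 at 120 per arm and higher at smaller sizes.
5. If the SAP sets a different primary threshold or an interim adjustment, pass on the corresponding level.

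The cost is wording and one exact calculation, with no extra patients or data and no test made stricter by the transfer. The rule is slightly more complex to describe, and the second arm's claims can then depend on the first arm's results.

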In Study MSB-DR003, each subject will be evaluated clinically at 1, 3, 6, 12, 18, 24 and 36 months after treatment. The primary analysis of safety and efficacy will be conducted at 24 months with a longer term assessment of safety and efficacy conducted at 36 months. Clinical assessments for Study MSB-DR003 will include those listed in Table 3. X-rays will also be taken at 1, 3, 6, 12, 18, 24 and 36 months after treatment and will consist of AP and lateral radiographs as well as flexion and extension x-rays. MRI scans will be taken at 12, 18, 24 and 36 months.

Surgical and injection interventions should be avoided through at least the 24 month primary endpoint follow-up. Surgical and injection interventions should only be undertaken if the subject's pain, measured by VAS, and function, measured by ODI, is not improved compared to the baseline values since an intervention could confound the efficacy assessments and would classify a subject as a treatment failure.

If a subject intends to undergo an intervention at the treated level, subjects should be encouraged to attend an unscheduled in-clinic visit for evaluation within 30 days prior to the new intervention (if a scheduled assessment does not already occur within that timeframe). During

this visit, all assessments and activities regularly performed at Visits 3-9 will be performed, with the exception of imaging assessments, hematology, chemistry panel, Flow Class I and II % PRA with specificity testing and DSA. If the subject's originally planned assessment timepoint falls within 30 days prior to the post-treatment intervention, the unscheduled visit will not be necessary.

It is strongly recommended that there be no changes (increase or decrease) from or additions to baseline pain medications (opioids, NSAIDs, aniline analgesics etc.). This is designed to minimize possible confounding treatment effects due to alterations in pain medications. Furthermore, it is suggested that subjects do not schedule any medical procedures which would require an adjustment in pain medications during the 2 weeks prior to any study visit. Subjects not taking opioids at baseline should similarly refrain from starting opioid treatment. However, should a significant increase in pain from baseline occur, as determined by a VAS score greater than baseline, the subject should be provided appropriate pain relief. Should there be any deviation from the baseline dose, information regarding the deviation must be documented.

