4.6.1 Lost to Follow-Up

A subject is considered to have been lost to follow-up if he/she is unable to be contacted by the investigator post-randomization. The investigator should show "due diligence" by documenting in the source documents steps taken to contact the subject, e.g., dates of telephone calls or registered letters. The end of participation for a subject lost to follow-up is the date of the last known contact (e.g., visit or telephone contact).

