6.3 Missing or Delayed Study Visits

Subjects should be encouraged not to miss any visits. Any visits that are missed or not completed within the specified timeframe (or window allowance) should be documented by the site and the CRA should be notified.

If a scheduled in-clinic visit is missed, the site should contact the subject to determine if any interventions that would classify the subject as a treatment failure have occurred since their last visit. If any interventions are reported, the site should collect all the information required if the intervention had been reported at an in-clinic visit. All intervention information collected remotely must be documented in a source document and/or worksheet.

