For the time to first intervention (since study injection), a Kaplan-Meier analysis will be used. The overall treatment comparison and each active treatment group versus the saline control group, as well as between the two active treatment groups for time to first adjudicated intervention will be analysed using a log-rank test, stratified by study (or pooled) sites. The following Kaplan-Meier point estimates of time to first adjudicated intervention and their corresponding 95% confidence intervals (CI) will be presented: 25th percentile, median, and 75th percentile. Kaplan-Meier curves to illustrate the differences among the treatment arms will be provided. Subjects who did not receive post-treatment intervention and subjects who withdraw or are lost to follow-up will be censored at the last performed visit

CONFIDENTIAL

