12.2.1 Post-treatment Interventions at the Treated Level

As one of the criteria defining some of the primary endpoints, post-treatment interventions should be reported in a consistent manner. In order to maintain standardized classification of these interventions, the TEC will be used. The TEC will evaluate all interventions after the treatment procedure to determine if an intervention has occurred at the treated level, indicating a failure of the treatment to provide symptomatic improvement ("treatment failure"). TEC Members will also have an opportunity to identify post-treatment interventions that may not have been reported previously.

Following is a list of procedures at the index level that will be considered an intervention and treatment failure for responder analyses:

Surgical Interventions

- Spine fusion, interbody or posterolateral
- Artificial Disc Replacement
- Interlaminar or Spinous Process Stabilization Device Implantation
- Discectomy
- Surgical Disc Decompression, including minimally invasive decompression procedures such as mild®
- Laminectomy
- Laminotomy
- Osteotomy
- Foraminotomy
- Facetectomy
- Facet Joint Ablation/Denervation/Rhizotomy
- Disc nucleoplasty
- Spinal cord stimulation
- Intradiscal Electrothermal Annuloplasty
- Intradiscal Ablation Procedures
- Intrathecal pump implantation.

Spine Injections

- Epidural steroid injections
- Transforaminal injection of corticosteroid
- Injection of any anesthetic, analgesic steroid or other potential pain relieving substance into the disc
- Facet Injection of corticosteroid.

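### Time to first intervention keeps events found after a subject's last visit but drops event-free time after it, so risk is overstated when final visits are missed and the subject is still reached

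*Combined protocol and SAP*

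**What the plan says.** Four parts of the protocol bear on this.

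- **Endpoint (9.4.2 and 9.6.3, sixth of six ordered secondaries).** "Measured as time to first post-treatment intervention at the treated level through 24 months post-treatment". It is not limited to interventions reported in clinic or dated before the last visit.
- **Censoring (9.6.3).** Subjects without an intervention, and "subjects who withdraw or are lost to follow-up will be censored at the last performed visit".
- **Missed visits (6.3, repeated in 3.1 and 9.9).** For anyone who does not attend as scheduled, the instruction is: "the site should contact the subject to determine if any interventions that would classify the subject as a treatment failure have occurred". The question covers the whole period after the previous attendance. A positive answer then has its own instruction: "If any interventions are reported, the site should collect all the information required if the intervention had been reported at an in-clinic visit".
- **Late identification (12.2.1).** "TEC Members will also have an opportunity to identify post-treatment interventions that may not have been reported previously".

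The visits are widely spaced: "each subject will be evaluated clinically at 1, 3, 6, 12, 18, 24 and 36 months after treatment". From Month 6 on, the gap between visits is at least six months. Section 9.6.3 plans a log-rank test stratified by site, Kaplan-Meier curves, and Kaplan-Meier estimates of the 25th, 50th and 75th percentiles. Section 4.6.1 adds, for subjects lost to follow-up: "The end of participation for a subject lost to follow-up is the date of the last known contact", and gives a telephone call as an example of contact.

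**The concern.** A censoring rule is harmless when the date on which follow-up stops does not depend on what happens afterwards. Here it can. Take a subject still enrolled who misses the last visits before Month 24 and answers the site's call. If an intervention is reported, it has a date after the last visit and falls within the endpoint definition. If none is reported, the same call has established event-free time, but the rule moves censoring back to the last performed visit. The risk set then loses only subjects known to be event-free, while every event stays in the numerator. The error can only be upward.

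At stake are the curves shown for each arm and, if the pattern of missed final visits differs between arms, the log-rank comparison.

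**Working it through.** **Inputs.** The visit times and the censoring and contact rules come from 3.1, 6.3 and 9.6.3; about 120 subjects per arm comes from 3.1. The documents state no intervention rate, missed-visit rate or contact rate, so there is no planned figure to reproduce. Assumptions: a true 24-month risk p of 10% or 20%, exponential event times, and a fraction m of subjects missing all visits from some point to Month 24.

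**Hand check.** Take 120 subjects with no events to Month 12 and 12 events after it (true risk 10%). Let 24 be last seen at Month 12, all later reached, with 10% of them (2.4) having an event. The other 24 − 2.4 = 21.6 are censored at Month 12. The risk set is 120 − 21.6 = 98.4, and the estimate is 12/98.4 = 12.2%, not 10.0%.

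**General formula, all reached.** Let S(t) = (1 − p)^(t/24), and let d(v) be the share of subjects whose last visit is at or before v. Between visit times v and w, the plan's Kaplan-Meier factor is

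1 − [S(v) − S(w)] / [S(v) − (1 − p)·d(v)].

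The term (1 − p)·d(v) is the event-free group that the rule removes too early.

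**Only Month 24 missed (last visit at Month 18).**

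- p = 10%: S(18) = 0.9^0.75 = 0.9240, and events from 18 to 24 are 0.0240. With m = 10% the risk set is 0.9240 − 0.09 = 0.8340, and the risk is 1 − 0.9240 × (1 − 0.0240/0.8340) = 10.3%. With m = 20% the risk set is 0.7440 and the risk is 10.6%.
- p = 20%: S(18) = 0.8459, and events are 0.0459. With m = 10% the risk set is 0.7659 and the risk is 20.5%. With m = 20% it is 0.6859 and the risk is 21.1%.

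**Visits stop at a random point (last visit at 1, 3, 6, 12 or 18 months, each with share m/5).** For p = 10% and m = 10%, each stopping point removes 0.9 × 0.02 = 0.018:

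| Interval (months) | Events | Risk set under the plan | Cumulative survival |
|---|---|---|---|
| 0–1 | 0.0044 | 1.0000 | 0.9956 |
| 1–3 | 0.0087 | 0.9776 | 0.9868 |
| 3–6 | 0.0129 | 0.9509 | 0.9734 |
| 6–12 | 0.0253 | 0.9200 | 0.9466 |
| 12–18 | 0.0247 | 0.8767 | 0.9199 |
| 18–24 | 0.0240 | 0.8340 | 0.8934 |

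The estimated risk is 1 − 0.8934 = 10.7%. The same steps give:

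| True risk | m = 10% | m = 20% |
|---|---|---|
| 10% | 10.7% | 11.4% |
| 20% | 21.2% | 22.5% |

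Simulation agrees to about 0.1 point. A wider simulated range (10–30% affected, 50–100% of them reached) gives 10.4–12.3% for a true 10% and 20.5–24.2% for a true 20%.

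**Where there is no bias (simulated).** With an interior visit missed but Month 24 attended, estimates are 9.9–10.1% and 19.9–20.0%. With final visits missed and nobody reached, a true 20% is estimated at 20.1%.

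**Log-rank test.** This was simulated with 120 per arm, unstratified, 20% risk in both arms, all reached, and 6,000 trials. The 0.9875 threshold is taken as a one-sided level of 1 − 0.9875 = 1.25%.

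| Final visits missed, active / control | False finding for active | False finding against active |
|---|---|---|
| 20% / 20% | 1.0% | 1.3% |
| 10% / 25% | 2.7% | 0.5% |
| 25% / 10% | 0.4% | 3.3% |

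**After the change.** With censoring at last known status, the risk set in the formula becomes S(v), the product telescopes to 1 − p, and the bias is zero. Simulated log-rank error returns to 1.0–1.3%.

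**The case against.** The strongest reply is that 9.6.3 never says that an intervention learned by contact enters this analysis. The missed-visit contact is described in treatment-failure terms, which belong to the responder analyses. Read literally, the censoring sentence also stops withdrawn and lost subjects at the last visit whatever is learned later, which treats events and event-free time alike. A subject lost to follow-up under 4.6.1 is by definition not contactable. The protocol also refers to the SAP for further detail on missing data, and no SAP text on this endpoint is in the document reviewed; an event cut-off could be there.

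Much of this stands. Entry of contact-found events is inferred from 6.3, 9.6.3 and 9.9 together. But the endpoint covers any first intervention through 24 months, with no limit by source, and nothing says that a documented contact counts as a performed visit. The asymmetry remains for subjects still enrolled who miss their final visits and answer.

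The bias is also small against sampling error. At 120 per arm the standard error is √(0.1 × 0.9/120) = 2.7 points at 10% risk and √(0.2 × 0.8/120) = 3.7 points at 20%. No 24-month Kaplan-Meier risk is listed as an output, and at these risks even the 25th percentile would not normally be reached. The effect would show mainly in the curves.

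A reader might infer that 4.6.1 contradicts 9.6.3. It does not: one dates the end of participation, the other sets an analysis censoring date. The dates differ, but the purposes do too.

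**Conclusion.** The point holds in a limited form and is minor. As written, the rule overstates intervention risk for subjects whose visits stop before Month 24 and whose status is learned afterwards, by contact or through the Treatment Events Committee. With 10–20% of subjects affected and all reached, the overstatement is about 0.7–1.4 points on a true 10% and 1.2–2.5 points on a true 20%. If only Month 24 is missed, it is about 0.3–0.6 and 0.5–1.1 points. These figures rest on assumed rates and on the reading that contact-found interventions count as events.

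Two stronger readings are tempting. One is that risk is overstated wherever a visit is missed. A later attended visit puts the last performed visit beyond the gap, and a subject never reached contributes neither late events nor late event-free time, so neither causes bias. The other is that the treatment comparison is biased. With equal missed visits the log-rank error stays near nominal. It moves only if missed final visits differ by arm, and the documents give no reason to expect a particular direction. The endpoint is also last in the hierarchy, so confirmatory use requires the primary and five earlier secondaries to succeed.

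**What to change.** In 9.6.3 and the SAP, censor event-free subjects at the earlier of Month 24 and the last date on which intervention status is known, whether from a visit or a documented contact. Count events only up to that same follow-up limit. State whether interventions identified later by the Treatment Events Committee are subject to the same limit.

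The text change is a sentence or two. The real cost is data capture. Section 6.3 requires documentation of intervention information collected remotely, but does not clearly require the date of a contact at which none is reported. The date and result of every contact, including negative ones, would need to be recorded in a form that the analysis can use.
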